**Table 2 Events Ending Follow-up and Censoring Variables**

		Operational Definition
Events ending follow-up, throughout the follow-up		
1	End of 24-month follow-up	2 years from end of initiation grace period for each patient
2	Death	For THIN Italy and Belgium: last contact date, which defines exit from the database regardless of reason (death, physician change, or choosing to exit the database) For Inspur China: Date of death directly available by a report from social security sent to Inspur
3	Loss to follow-up/exit of data source	For THIN Italy and Belgium: last contact date, which defines exit from the database regardless of reason (death, physician change, or choosing to exit the database) For Inspur China: Date of lost to follow-up, which defines exit from the database regardless of reason (death or migration to another city)
Censoring during follow-up, after the 30-day initiation grace period: deviation from the assigned treatment strategy		
1.1	OM-85 group: None	-
1.2	SOC/non-user group: at first date of OM-85 prescription during follow-up (after the initiation grace period)	Same
1.3	Sensitivity analysis: The SOC/non-user group are censored at the first date of prescription for any bacterial lysate (including OM-85), the OM-85 group would be censored at the first date of prescription of any bacterial lysate other than OM-85 during follow-up	Same

Note: CED: cohort entry date; SOC: standard of care; THIN: The Health Improvement Network.

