#### 3.3.1 Exposures

To investigate the effectiveness of OM-85 using the TTE framework, the other clinically relevant treatment strategy that OM-85 will be compared to needs be defined, i.e., a treatment strategy that the patients prescribed OM-85 could alternatively have (28,29). This alternative treatment strategy to patients who initiated OM-85 is defined as “not initiating OM-85”, which will represent a SOC/non-user group (Table 6).

A 30-day initiation grace period starting from the CED will be applied for each included patient (Section 3.2.1), to allow the included patients to initiate OM-85 during a reasonable period after the CED, as it is unrealistic to expect that OM-85 would in clinical practice be prescribed on the date of meeting the eligibility criteria (28,29). Patients will be ascertained as treated or untreated depending on whether they received a prescription for OM-85 during the grace period.

After the patients have been categorised to one of the treatment strategies during the initiation grace period, the OM-85 treatment strategy will be considered static and no censoring will be applied due to “deviation from the treatment strategy”. Censoring at initiation of other treatments for RTI will not be applied, because patients initiating OM-85 are typically prescribed RTI

treatments as part of RTI treatment pathway, including symptomatic measures and/or antibiotics. In other words, patients in clinical practice may be prescribed other treatments in parallel with OM-85. Therefore, censoring at initiation of another therapy would not be a deviation from the OM-85 treatment strategy. Censoring OM-85 at discontinuation will also not be applicable, because OM-85 is not used continuously in clinical practice, but rather as 3-month or 6-month courses (consisting of monthly 10-days treatment periods). Consequently, all patients initiating OM-85 will be followed-up regardless of initiation or parallel use of other therapies.

The frequency of RTI episodes could be impacted by other treatments taken during the follow-up. However, it is likely that most patients co-medicate over the course of RTI episodes, which would lower the magnitude of effect. To address this limitation, the results will be interpreted considering observed other treatments than the index drug during the follow-up period.

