In the SOC/non-user group, patients are censored at the date of observing a record of an OM-85 prescription, as the SOC/non-user patients would then deviate from their treatment strategy.

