**Table 6 Treatment Strategies (Exposure Groups)**

OM-85 group	Patients initiating preventive treatment with OM-85	Initiation of OM-85 at CED or 30 days after (during the 30-day initiation grace period), defined at the first observed prescription of OM-85 during this time, using country-specific drug codes ( Appendix 4 ) The patients are “new users”, as no prescriptions of any bacterial lysates are allowed in the 12-month baseline period. Preventive treatment is considered static; no censoring is applied in follow-up at deviation from treatment strategy. In a sensitivity analysis, patients will be censored at date of the first prescription of another bacterial lysate ( Section 3.7.7 ).
SOC/non-user group	Patients not initiating OM-85	SOC/non-user group: No initiation of OM-85 at CED or 30 days after (during the 30-day initiation grace period). Censoring at first record of OM-85. In a sensitivity analysis, patients will also be censored at date of the first prescription of another bacterial lysate than OM-85 ( Section 3.7.7 ).

Note: CED: cohort entry date; SOC: standard of care.

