30-day initiation grace period. Patients will be censored from the cloned OM-85 exposed group at the end of the 30-day initiation grace period, if no prescription of OM-85 is observed by then. Patients will be censored from the cloned SOC/non-user group, if a prescription of OM85 is observed during the 30-day initiation grace period (censoring at the date of the prescription). Artificial censoring of the clones when they deviate from their treatment assignment could create potential selection bias due to informative censoring, and thereby inverse probability weighting will be applied to adjust for potential risk of informative censoring, after the CED. The weights are implemented, because not receiving an OM-85 prescription during the 30-day initiation grace period (and thus being censored) is likely not at random, but influenced by variables that could also impact the outcome (confounders) (37). The censoring weighs up the influence of the patients who remain uncensored to account for similar patients who were censored, breaking the association between censoring and variables that may cause the outcome. The variables included in the weighting can include baseline variables and time-varying confounding variables that could change during the 30-day initiation grace period, such as healthcare resource utilisation (e.g. hospitalisation) or receiving a diagnosis of a respiratory condition. Description of baseline as well time-varying variable that change during the initiation grace period will be described and compared in user and non-user groups. The time-varying variables will be selected from the list of baseline factors (as listed above for PS), but they are measured also after CED. These variables will be further defined in the SAP. The cloning and censoring are illustrated in [Figure 3](#).

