Protocol component	Target trial specification (hypothetical)	Target trial emulation for a non-interventional (observational) cohort study using healthcare databases	Justifications
	
 
24 months from randomisation, death, or loss to follow-up, whichever occurs first
 
	
 
End of maximum 24-month follow-up, death, or loss to follow-up/exit of data source, whichever occurs first
 
	
Causal contrasts	Intention-to-treat effect	Observational analogue of per-protocol effect	Intention-to-treat is not possible when the assignment is not known at CED
Statistical analysis	Intention-to-treat analysis	
Intention-to-treat [modified] analysis
 
 
Treatment assignment will be ascertained according to whether the patient received OM-85 during the initiation grace period.
 
The SOC/non-user group will be censored at first date of OM-85 prescription during follow-up (after the initiation grace period)
 
In sensitivity analysis for primary objective 2, clone-censor weighting which is a per-protocol approach will be conducted.
 
	;

Note: CCI [redacted]; CED: cohort entry date; CCI [redacted]; PS: propensity score; SOC: standard of care; RTI: respiratory tract infection.

- OM Pharma SA. Investigator’s Brochure OM-85 Respiratory Tract Infections. 11th ed. 2023.

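### Table 13 names two different effects for primary objective 2, and the one-sided censoring of SOC patients at OM-85 start over 24 months has no described correction

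*Protocol*

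**What the plan says.** **Censoring rule.** Table 2 lists the deviation rule for the main analysis as "OM-85 group: None" on one side and, on the other, "SOC/non-user group: at first date of OM-85 prescription during follow-up (after the initiation grace period"). Section 3.3.1 gives the reasons. OM-85 is used in courses, so "the OM-85 treatment strategy will be considered static and no censoring will be applied" for that group, whereas a later OM-85 prescription in a SOC patient counts as leaving the strategy: "In the SOC/non-user group, patients are censored at the date of observing a record of an OM-85 prescription". Follow-up runs up to 24 months from the end of the 30-day grace period.

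**SOC strategy.** Table 6 defines it as "No initiation of OM-85 at CED or 30 days after (during the 30-day initiation grace period"), and Table 13 likewise ties it to the grace period. Both then apply the later censoring.

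**Effect and analysis.** In Table 13 the emulated causal contrast is "Observational analogue of per-protocol effect", with the justification "Intention-to-treat is not possible when the assignment is not known at CED". The next row calls the analysis intention-to-treat (modified), lists the SOC censoring beneath it, and describes the clone-censor-weight sensitivity analysis as the per-protocol approach.

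**Model.** Sections 3.7.1 and 3.7.3 specify a Poisson or negative binomial model in the PS-matched sample, with the exposure flag as independent variable, a log time-at-risk offset and cluster-robust standard errors.

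**Weights.** They appear only in Section 3.7.7, for the clone-censor-weight analysis. There the protocol warns: "Artificial censoring of the clones when they deviate from their treatment assignment could create potential selection bias due to informative censoring". The deviations it describes are those judged within, or at the end of, the 30-day grace period.

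**The concern.** There are two linked problems.

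First, the contrast row and the analysis row of Table 13 do not describe the same quantity. A per-protocol contrast asks what would happen if SOC patients stayed off OM-85. An intention-to-treat analogue compares the groups as classified at the end of the grace period, whatever they take later. The reason given for ruling out intention-to-treat refers to the CED, but main follow-up starts at the end of the grace period, when every patient's group is known.

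Second, the operational rule is the per-protocol one, and that brings the problem the protocol itself names in Section 3.7.7. OM-85 is prescribed because RTIs recur, so SOC patients who start it later may well be those with higher RTI rates. Removing their remaining time lowers the SOC rate. A log-time offset allows for shorter follow-up, but not for who leaves. Matching on baseline covariates cannot correct selection that arises during follow-up. The effect would accumulate with time, so the 24-month result is more exposed than the 12-month result.

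**Working it through.** **1. The plan's own figure.** The only precision figures are in Table 9, for primary objective 1. With 350 person-years per group, 2 episodes per person-year and IRR 0.9, b = 700 and a = 630. The F-quantile formula in Section 3.5 gives a 95% CI width of 0.1968, against 0.197 stated; all 32 cells reproduce. No figure is wrong, and none is given for primary objective 2.

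**2. Inputs for the illustration.**
- Mean RTI rate 2 per person-year: Section 3.5, where it is hypothetical.
- Follow-up 2 years: Table 2.
- Share of SOC patients censored at OM-85 start: **not in the document**; 1% to 30% assumed.
- Spread of individual rates L: **not in the document**; gamma with shape 1 or 2 assumed (Section 3.7.3 allows for over-dispersion).
- True drug effect: none, so an unbiased IRR is 1.00.

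**3. Formula.** Each RTI leads to OM-85 start, and so to censoring, with probability q. Expected time at risk is T(L) = (1 − exp(−2qL))/(qL). The observed SOC rate, events over person-time, is E[L·T(L)]/E[T(L)], and the null IRR is 2 divided by that rate. For each censored share, q solves 1 − E[exp(−2qL)] = share.

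**4. Worked case: shape 1, 10% censored.**
- 1 − 1/(1 + 4q) = 0.10, so q = 1/36 = 0.0278.
- E[L·T] = 0.10/0.0278 = 3.60.
- E[T] = ln(1 + 4q)/(2q) = 0.1054/0.0556 = 1.897.
- SOC rate = 3.60/1.897 = 1.898; IRR = 2/1.898 = 1.05.

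**5. Results** (no drug effect; 12-month columns use the same q):

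| SOC censored by 24 months | 24-month IRR, shape 1 / 2 | 12-month IRR, shape 1 / 2 |
|---|---|---|
| 1% | 1.005 / 1.003 | 1.003 / 1.001 |
| 5% | 1.03 / 1.01 | 1.01 / 1.01 |
| 10% | 1.05 / 1.03 | 1.03 / 1.01 |
| 20% | 1.12 / 1.06 | 1.06 / 1.03 |
| 30% | 1.19 / 1.09 | 1.10 / 1.05 |

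If all patients share one rate, the IRR is 1.00 at every share.

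**6. Separate simulation** (400,000 SOC patients per scenario, true IRR 0.90, q = 5%, about 17% censored by 24 months). The SOC rate falls from 2.0 to 1.91 (shape 2) or 1.83 (shape 1), so the IRR appears as 0.9 × 2/1.91 = 0.94 or 0.9 × 2/1.83 = 0.98. With no rate variation it stays at 0.90.

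**7. Dependence on the model.** The table applies to the ratio of crude rates, which is what a Poisson model with only the exposure flag and offset returns. I also fitted a negative binomial model with offset to simulated data (300,000 per group, no drug effect, 20% censored). When OM-85 start depends only on recorded RTIs and rates are exactly gamma, its IRR is 1.00. When start depends on the patient's underlying rate rather than on recorded episodes, it is 1.06 (shape 1) or 1.04 (shape 2), against 1.11 and 1.06 for Poisson.

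**The case against.** **One-sided censoring is not in itself an error.** A reader might infer that it is. Section 3.3.1 explains why the OM-85 strategy has no deviation to censor, and the rule suits initiating versus never initiating. This stands: the fault is the absence of any described correction together with the conflicting labels.

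**The SAP may add weights.** Section 3.7 defers detailed methods to it, and Section 3.9.1.2 says further analyses of bias will be considered there. Nothing rules weights out. That limits the second problem, but not the first: an SAP cannot make two rows of the protocol agree. The protocol also says where weights are used and does not extend them to this censoring.

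**The analysis can be followed.** The censoring rule is the same in Section 3.2.1, Tables 2, 6 and 13, and Section 3.3.1. That is correct: the procedure is clear, but the effect it is meant to estimate is not. It is also literally true that assignment is unknown at the CED; the sentence simply does not fit a follow-up that starts 30 days later.

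**The size rests on assumptions.** One might infer from Section 3.9.5, where random choice of the CED can place OM-85 users in the non-user group, that crossover will be substantial. That section speaks only of a risk and gives no share. The feasibility counts do not settle it: 14,362/500,000 = 2.9% in Belgium and 3,219/550,000 = 0.6% in Italy use whole-database yearly denominators, not matched patients with recurrent RTIs. A negative binomial model could also remove part or all of the bias (step 7), and matching may narrow the spread of rates.

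**A hidden benefit is not shown.** A reader might infer that a real effect would be masked. At small crossover shares the result is slight attenuation, and in these scenarios the bias runs against OM-85, so it would not create a false benefit.

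**Conclusion.** The point holds as a defect in how primary objective 2 is specified. Table 13 pairs a per-protocol contrast with an analysis labelled modified intention-to-treat, on a justification that does not fit the current start of follow-up. The rule actually applied censors SOC patients for 24 months without a described correction, although the protocol accepts elsewhere that such censoring can be informative.

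That it is informative here is an inference, but the protocol supports it. Initiators are expected to have more prior RTIs (Section 3.2.2.1), the SOC group is heterogeneous in RTI frequency and severity (Section 3.3.1.1), and receipt of OM-85 in the grace period is thought not to be random (Section 3.7.7).

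The size cannot be fixed from the document. Under the stated assumptions the null 24-month crude or Poisson IRR ranges from about 1.003 at 1% censored to 1.19 at 30%. It is smaller at 12 months, smaller or absent under a negative binomial model, and 1.00 without rate variation. For scale, the protocol's own small effect is an IRR of 0.9. A correction is worth making; a material bias is possible but not demonstrated.

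**What to change.** Name one estimand for primary objective 2 and make the contrast, justification and analysis rows of Table 13 agree with it.

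- **If per-protocol** (initiate versus never initiate): extend the SOC strategy in Tables 6 and 13 beyond day 30, keep the censoring, and add inverse-probability-of-censoring weights for OM-85 start through month 24. Use time-updated RTI count, antibiotics and visits as available in each database.
- **If an intention-to-treat analogue** (initiate within 30 days or not): do not censor SOC patients at later OM-85, and replace the justification that refers to the CED.

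Report the other as a sensitivity analysis, with the number and timing of SOC crossovers by country so that readers can judge the scale.

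The cost is revised wording, one weight model and some added variance. The weights would rest on incomplete covariates: THIN lacks hospital and emergency data, and Inspur lacks primary care. The uncensored analysis has its own drawback, since later OM-85 use in the SOC group would dilute any effect. That is a reason to show both.

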**Table 6 Treatment Strategies (Exposure Groups)**

OM-85 group	Patients initiating preventive treatment with OM-85	Initiation of OM-85 at CED or 30 days after (during the 30-day initiation grace period), defined at the first observed prescription of OM-85 during this time, using country-specific drug codes ( Appendix 4 ) The patients are “new users”, as no prescriptions of any bacterial lysates are allowed in the 12-month baseline period. Preventive treatment is considered static; no censoring is applied in follow-up at deviation from treatment strategy. In a sensitivity analysis, patients will be censored at date of the first prescription of another bacterial lysate ( Section 3.7.7 ).
SOC/non-user group	Patients not initiating OM-85	SOC/non-user group: No initiation of OM-85 at CED or 30 days after (during the 30-day initiation grace period). Censoring at first record of OM-85. In a sensitivity analysis, patients will also be censored at date of the first prescription of another bacterial lysate than OM-85 ( Section 3.7.7 ).

Note: CED: cohort entry date; SOC: standard of care.

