**Table 4 Inclusion Criteria**

	Inclusion Criteria	Operational Definition
1	Patient aged $\geq 1$ year of age at CED	Aged $\geq 1$ year at CED
2	Patient has $\geq 1$ RTI episodes during the 12-month baseline period prior to CED	$\geq 1$ RTI episodes within a 12-month period during the inclusion period. The CED is the date of the 2 nd , 3 rd , ... or n th RTI episode (i.e., date of fulfilling the inclusion criteria). If one patient has multiple CED during the inclusion period, the CED will be selected randomly. The definition of an RTI episode provided in Section 3.3.2.1
3	Patient has $\geq 12$ months of continuous enrolment in the database prior to CED	$\geq 12$ months of continuous enrolment in the database prior to the CED. Operationally, patients were required to have entered the database at least 12 months before the CED to be included in the study. In THIN (Belgium and Italy), this can be defined by a district variable for entry to the database: first contact date. In Inspur (China), patients are required to have records in the database at least 12 months before the CED (during the 12-month baseline period) to be eligible for inclusion
4	No record of a prescription of any bacterial lysates in the 12-month baseline period prior to CED	No record of the country-specific drug codes ( Appendix 4 ) during the 12-month baseline period

Note: CED: cohort entry date; RTI: respiratory tract infection; THIN: The Health Improvement Network.

Inclusion criterion 2 on the requirement of having  $\geq 1$  prior RTI episodes is important to apply because OM-85 is indicated for prevention of recurrent RTIs (24). However, patients in the SOC/non-user comparator group may still have fewer prior recurrent RTIs than the OM-85 group receiving preventive therapy. Therefore, prior recurrent RTIs will also be used in the PS matching of the compared exposure groups. The impact (preventive effect) of OM-85 on the recurrence of RTIs is anticipated to be higher in patients with an increased recurrence risk (35). Hence, the analyses will also be stratified by the number of RTI episodes prior to CED (see [Table 5](#)).

The inclusion of patients is not defined by sex. Sex is instead defined at CED and considered in the PS.

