### 3.3.3 Other Variables

Selected baseline variables described under outcomes ([Section 3.3.2.2](#)) will be assessed in the Step 1 analysis and will be used for controlling for confounding at baseline, through including the selected variables to the PS and matching OM-85 initiators to non-initiators (SOC/non-user group) using the PS. The following baseline variables will be considered in the PS:

- Patient demographics: Age and sex
- BMI
- RTI history, including type (Upper/Lower/Other) and number of previous RTI episodes
- Comedications
- Antibiotic prescriptions
- Selected comorbidities, especially smoking and respiratory conditions, such as asthma, COPD, and CB
- Overall and RTI-specific healthcare resource utilisation, especially duration of RTI-related hospitalisation(s) as a proxy for severity of prior RTIs
- Calendar year of CED

The confounders applied in the PS will be detailed in the SAP.

Variables used for defining sub-populations are described in [Section 3.2.2.3](#).

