### 3.9.3 Selection Bias

Selection bias refers to the selective inclusion of patients who are not representative of exposure or outcome in the source population, causing distortion in the exposure -outcome relation.

No selection bias is anticipated to emerge from the use of the healthcare databases, which were selected based on a thorough feasibility assessment. While the two European data sources include patients treated in primary care, this type of patients is limited in Inspur (China) where mostly secondary and tertiary care data are available. The combination of the three data sources will provide a wide coverage of the source population in terms of health settings.

Selection bias due to differing settings for the compared exposure groups is not a threat in this study, because both exposure groups are included from the same source populations and time periods, within each country. Further, no selection bias is anticipated to emerge from the application of the inclusion criteria, as availability and data quality of the inclusion criteria in the databases was assessed in the feasibility study.

Further, selection bias is reduced by including in the OM-85 exposure group exclusively patients initiating preventive treatment with OM-85, i.e., new users only, using the 12-month baseline period as a washout when no prescriptions of bacterial lysates are allowed. Including prevalent users (patients with a previous record of OM-85 in the 12-month baseline period) would have two implications:

- Healthy-user or adherer bias, as the included prevalent users would be patients who did not experience early adverse events or lack of early effectiveness.
- The effect against RTI would in reality start before the index date and this effectiveness would not be captured, and therefore the overall effectiveness of OM-85 could be decreased in the results.

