### 3.9.4 Time-Related Biases

Time-related biases were minimised by designing the study using the TTE framework (28,29). Importantly, follow-up was carefully selected to start at the end of the initiation grace period, equally for both exposure groups to eliminate immortal time bias. Starting follow-up at OM-85 initiation date for the OM-85 groups, and at CED for the SOC/non-user group would inevitably result in immortal time bias.

The initiation grace period was defined as 30 days, based on alignment with clinicians on a reasonable time for prescribers to prescribe preventive treatment with OM-85 after an RTI. Alternative grace periods may be considered in the SAP.

The time windows to detect the outcomes during the follow-up were chosen based on evidence from interventional studies on OM-85 with up to 12-month follow-up (24). In this study in real-world settings, follow-up was extended to 24 months, with the opportunity to investigate longer-term effectiveness and thereby complement the results of interventional studies. No bias is anticipated from this maximum 24-month window to detect outcomes.

The OM-85 treatment strategy was considered static (Section 3.3.1), based on its clinical use. However, in the static treatment strategy in the main analysis, OM-85 initiators will not be censored if/when they are prescribed other bacterial lysates during the follow-up. While this is consistent with the chosen treatment strategy, the time window for detecting the outcomes associated with OM-85 is not free from the effect of other bacterial lysates. Therefore, censoring follow-up at the first date of a prescription of another bacterial lysate will be applied in a sensitivity analysis, for both exposure groups.

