## 8.7 Appendix 7: Target Trial Specification and Emulation

**Table 13 Target Trial Specification and Emulation**

Protocol component	Target trial specification (hypothetical)	Target trial emulation for a non-interventional (observational) cohort study using healthcare databases	Justifications

Eligibility criteria
	
Inclusion criteria
 
 
• Aged <math>\geq 1</math> year at enrolment
 
• <math>\geq 1</math> RTI episodes within 12 months prior to enrolment
 
• No use of any bacterial lysates 12 months prior to enrolment
 
 
Exclusion criteria None.
	
Same, using the operational definitions for a secondary data.
 
Inclusion criteria
 
 
• Aged <math>\geq 1</math> years during the inclusion period
 
• <math>\geq 1</math> RTI episodes within a 12-month period during the inclusion period. The CED is the date of the 2nd, 3rd, ... or nth RTI episode (i.e., date of fulfilling this inclusion criterion)*
 
• <math>\geq 12</math> months of continuous enrolment in the database prior to the CED
 
• No record of prescription of any bacterial lysates within 12-months prior to the CED
 
 
Exclusion criteria None
 
* During the inclusion period, patients can have several CED. For these patients, the CED will be selected randomly, which is one of the unbiased methods to select the date. Patients are allowed to enter the study only once.
	
Inclusion criteria
 
 
• OM-85 is approved from 6 months of age. However, at minimum 12 months of baseline data are needed. Therefore, the minimum age at inclusion is 1 year.
 
• The included patients have to meet the indication for OM-85, to have as comparable exposure groups as possible. Hence, recurrent RTIs have to be an inclusion criterion.
 
• In the non-interventional study, a minimum of 12 months of baseline data are needed for each patient, for defining the inclusion criterion of no use of any bacterial lysates, baseline characteristics, and the rate of RTI episodes before inclusion to the study. This criterion would not be applied in a trial.
 
• Prescriptions of any bacterial lysates is not allowed, in order to include only new users of OM-85 and isolate the effectiveness of OM-85 from other bacterial lysates. Apart from OM-85, other bacterial lysates may have (partially) corresponding effect, and hence included patients will also have to be naïve to them. The term “prescription” is used because the available databases include prescription data.
 
 
Exclusion criteria
 
 
• No exclusion criteria are defined, because none of the considerations and precautions for OM-85 use described in the product information, such as pregnancy or hepatic and renal impairment, are strict contraindications for OM-85.
 

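### A 12-month lysate-free window does not establish new use of OM-85, and earlier lysate courses are neither measured nor discussed although both primary objectives run to 24 months

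*Protocol*

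**What the plan says.** Table 4, criterion 4, requires "No record of a prescription of any bacterial lysates in the 12-month baseline period prior to CED". Three conclusions are drawn from this rule:

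- Table 6 calls the OM-85 patients new users on the ground that "no prescriptions of any bacterial lysates are allowed in the 12-month baseline period".
- Table 13 justifies the criterion "in order to include only new users of OM-85 and isolate the effectiveness of OM-85 from other bacterial lysates". It adds, about lysates other than OM-85, "hence included patients will also have to be naïve to them".
- Section 3.9.3 treats the 12-month window as the washout that keeps out prevalent users, and defines a prevalent user by an OM-85 record inside that window. One harm it wants to avoid is a group made up of "patients who did not experience early adverse events or lack of early effectiveness". The other is an effect that begins before the index date.

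On the effect window, section 3.9.4 says the cited interventional studies had up to 12 months of follow-up, and that here "follow-up was extended to 24 months, with the opportunity to investigate longer-term effectiveness". Section 3.3.1 makes the OM-85 strategy static, so an initiator's time is not censored when a course ends.

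On adjustment, section 3.3.3 opens its list with "The following baseline variables will be considered in the PS". The list covers demographics, BMI, RTI history, comedications, antibiotics, comorbidities, healthcare use and calendar year. The comedications defined in Table 8 contain no lysates and are measured over 12 months. The final PS variables are left to the SAP.

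**The concern.** Having no prescription for a year is a weaker property than being a new user or being naïve. The gap matters here for three reasons.

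First, OM-85 is given in courses (section 3.3.1), and Table 5 and section 3.3.1.2 provide for second cycles, so a return after more than a year is an ordinary possibility.

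Second, the two harms named in section 3.9.3 apply equally to a patient returning after 13 months, whom the rule admits.

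Third, the CED is drawn at random from inclusion periods that run from 2006 to 2022 in Belgium and from 1995 to 2022 in Italy. Section 3.9.5 concedes that an unselected CED may be the one that led to OM-85. If that course was more than 12 months before the selected CED, the patient can enter as a non-user.

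At stake are the *before* rate in primary objective 1, and the contrast and the balance of the groups in primary objective 2.

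**Working it through.** **Windows.** The protocol gives no figure for earlier lysate use, so the first check is on time windows.

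- Effect window 24 months minus washout 12 months leaves courses 12 to 24 months before the CED uncovered.
- *Primary objective 2.* Take a non-user with a course 13 months before the CED. Follow-up starts 30 days after the CED, about 14 months after that course. Months 14 to 24 after the course are then counted as non-user time, while the same months after initiation count as OM-85 time in the other group. Censoring in the non-user group is triggered only by a new OM-85 prescription during follow-up.
- *Primary objective 1.* For a course X months before initiation, with X between 12 and 24, the *before* year covers months X − 12 to X after that course. At X = 13 this is months 1 to 13; at X = 18 it is months 6 to 18. So the reference year of a returning user can overlap even a 12-month effect: the overlap is 24 − X months, that is 11 of 12 months at X = 13 and 6 of 12 at X = 18.

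**Size in primary objective 1.** Let r be the true IRR, p the share of initiators with an earlier course, and c the share of the log effect still present in the *before* year. Both p and c are assumptions; the documents give neither.

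Observed IRR = r / [(1 − p) + p·r^c]. With full persistence (c = 1) this is r / [1 − (1 − r)p].

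For r = 0.80:

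| p | c = 1 | c = 0.5 | c = 0.25 |
|---|---|---|---|
| 10% | 0.80/0.98 = 0.816 | 0.809 | 0.804 |
| 30% | 0.80/0.94 = 0.851 | 0.826 | 0.813 |
| 50% | 0.80/0.90 = 0.889 | 0.845 | 0.822 |

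For the same p values and c = 1, a true 0.70 becomes 0.722, 0.769 and 0.824, and a true 0.90 becomes 0.909, 0.928 and 0.947.

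**Allowing for the required baseline RTI.** Criterion 2 requires at least one RTI in the baseline year, which raises the *before* rate of returning users too. Assume Poisson counts and the section 3.5 rate of 2 per year. The mean given at least one episode is 2/(1 − e^−2) = 2.313. For a returning user with r = 0.70 and full persistence it is 1.4/(1 − e^−1.4) = 1.858. With p = 30% the *before* mean is 0.7 × 2.313 + 0.3 × 1.858 = 2.177, and 2.313/2.177 = 1.06. Without this allowance the factor is 1/0.91 = 1.10. The inflation of the IRR falls from about 10% to about 6%.

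**Against the planned precision.** The section 3.5 formula reproduces Table 9, including a 95% CI width of 0.197 at 350 person-years and an IRR of 0.9. Half of that is about 0.10. For a true 0.90 the shift ranges from 0.002 (p = 10%, c = 0.25) to 0.047 (p = 50%, c = 1). It lies within that half-width, but unlike random error it does not shrink as the sample grows.

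**The case against.** The case on the other side has substance.

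- *The PS covariates are not settled here.* The list is one of candidates, section 3.7.1 calls it not exhaustive, and the SAP fixes the final set. A reader might infer that earlier lysate use is excluded from the PS; the protocol does not say so. What stands is that it is not named, and that the variables that are named cannot capture it.
- *The definition is open.* Table 6 states its 12-month basis, section 3.9.3 uses the same window, and the hypothetical trial in Table 13 has the same criterion. A reader might infer that the protocol claims first-time use of OM-85. It never uses that term, and naïve in Table 13 refers to other lysates. Still, the benefits claimed for new use go beyond what the rule delivers.
- *A 24-month effect is the study's question, not its premise.* The cited trial evidence reaches 12 months, and the 24-month outcome includes re-treatment, so it is not pure carry-over from one course. This stands. It does not clear primary objective 1, where the *before* year can fall within 12 months of an earlier course.
- *The harm in primary objective 2 is not shown.* A reader might infer that returning users are past responders and so favour OM-85. Every entrant has a further RTI at the CED, so they could equally be past non-responders. The documents do not settle the direction.
- *The longer look-back is described for selected variables such as comorbidities.* Nothing shows that earlier lysate records are already in the extract.

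**Conclusion.** The point holds in a limited form. The 12-month rule supports the statement that no lysate was prescribed in the previous 12 months. It does not support new use of OM-85 or being naïve to other lysates, and it does not remove the two harms that section 3.9.3 attributes to earlier users. Patients with older courses can enter both groups, and the protocol provides no measurement, named adjustment or limitation for them.

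The size cannot be computed because the share of such patients is not given. In primary objective 1 a persisting effect pulls the IRR towards 1. A true 0.80 would be seen as at most about 0.82 to 0.89 for an assumed 10% to 50% of returning users with full persistence, and would be less distorted with decay or after allowing for the required baseline RTI. In primary objective 2, residual effect among non-users pulls towards 1, while selective return to OM-85 could act in either direction, so the net direction is unknown. This is a reason to measure earlier use; it does not show that the comparison is invalid.

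**What to change.** Keep the 12-month entry rule, and make four changes.

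1. Derive a yes/no variable for any bacterial lysate prescription before the 12-month window, using the available look-back. Report it by group under secondary objective 1 and name it as a PS candidate in section 3.3.3.
2. Add to section 3.7.7 a sensitivity analysis of both primary objectives, restricted to patients with at least 24 months of look-back and no earlier lysate record.
3. In Tables 6 and 13 and section 3.9.3, replace the new-user and naïve wording with a statement that no lysate was prescribed in the previous 12 months.
4. Add to section 3.9.3 the limitation that older courses are possible in both groups.

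The cost is one derived variable, one further analysis and a check that the extract includes older lysate records. The restricted sample will be smaller. Look-back is uneven: Inspur data start in January 2018, so patients with a 2019 CED cannot have 24 months, and Italian paediatrician data start in 2017. The length of look-back should therefore be reported beside the new variable, since an absent record means less where the history is short.
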